Vorinostat was evaluated in a panel of genetic toxicity assays; *in vivo* and *in vitro* assays were found to be positive. Therefore, vorinostat should not be taken by pregnant women. Both women and men of reproductive potential participating in vorinostat studies must be completely informed of the unknown risks of pregnancy and agree not to become pregnant or father a child during the time they are participating in the study until at least 30 days after the final dose. Further, appropriate contraception must be used.

Vorinostat-related Clinical or Laboratory Adverse Experiences by Preferred Term as experienced by \ge 10% of all Patients

	Total Patients (N=305)		
	Related Experiences Only		
	All Grades	Grade 3-5	
	n %	n %	
Fatigue	195 (63.9)	42 (13.8)	
Nausea	170 (55.7)	17 (5.6)	
Diarrhoea	151 (49.5)	14 (4.6)	
Anorexia	141 (46.2)	15 (4.9)	
Vomiting	100 (32.8)	5 (1.6)	
Hyperglycaemia	79 (25.9)	10 (3.3)	
Blood Creatinine Increased	75 (24.6)	2 (0.7)	
Weight Decreased	75 (24.6)	4 (1.3)	
Thrombocytopenia	69 (22.6)	34 (11.1)	
Constipation	54 (17.7)	3 (1.0)	
Dysgeusia	54 (17.7)	0 (0.0)	
Haemoglobin Decreased	53 (17.4)	10 (3.3)	
Dehydration	45 (14.8)	25 (8.2)	
Hypocalcaemia	42 (13.8)	3 (1.0)	
Platelet Count Decreased	41 (13.4)	13 (4.3)	
Dyspnoea	40 (13.1)	1 (0.3)	
Anaemia	36 (11.8)	7 (2.3)	
Hyponatraemia	36 (11.8)	5 (1.6)	
Alopecia	35 (11.5)	0 (0.0)	
Dry Mouth	35 (11.5)	0 (0.0)	
Aspartate Aminotransferase Increased	34 (11.1)	2 (0.7)	
Alanine Aminotransferase Increased	33 (10.8)	1 (0.3)	
Hypokalaemia	33 (10.8)	6 (2.0)	
Blood Alkaline Phosphatase Increased	31 (10.2)	1 (0.3)	
Hypoalbuminaemia	31 (10.2)	1 (0.3)	
White Blood Cell Count Decreased	31 (10.2)	4 (1.3)	
A patient is counted only once within a specific preferred term, even if more than one adverse experience with specific preferred term occurred. Adverse experience terms are from MedDRA Version 8.1			

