3.3.9.6 Temozolomide is potentially mutagenic and should be handled with appropriate precautions by both staff and patients. Capsules should not be opened. If capsules are accidentally opened or damaged, rigorous precautions should be taken with the capsule contents to avoid inhalation or contact with the skin or mucous membranes. Procedures for proper handling and disposal of anticancer drugs should be considered.

3.3.10 Contraindications: Temozolomide is contraindicated in patients who have a history of a hypersensitivity reaction to any of its components or to DTIC.

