3.3.11 Pregnancy Category D

Temozolomide may cause fetal harm when administered to a pregnant woman. There are no adequate and well-controlled studies in pregnant women. If this drug is used during pregnancy, or if the patient becomes pregnant while taking this drug, the patient should be apprised of the potential hazard to the fetus. **Women of childbearing potential should be advised to avoid becoming pregnant during therapy with temozolomide.**

Treatment of a man with temozolomide may increase the risk of birth defects if he causes a woman to become pregnant while he is taking temozolomide. Men treated with temozolomide may have difficulty causing a woman to become pregnant after their treatment is completed. Men receiving temozolomide should be directed to use effective contraception while they are being treated. There is insufficient data to know what the risk of subsequent problems with fertility will be. Similarly, women who are treated with temozolomide may have difficulty becoming pregnant in the future and may at be at increased risk of having children with birth defects. There is insufficient evidence to determine what the risk of these complications will be.

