- **4.13** Patients receiving valproic acid (VPA), an anticonvulsant drug with HDAC inhibitor properties, will be excluded, unless they are switched to an alternative agent prior to treatment initiation. No wash out period is required.
- **4.14** Prior treatment with dose dense regimens of temozolomide is not allowed (e.g, 7 days on/7 days off, 21 day/28 day and daily low dose continuous dosing). However, standard day 1-5 dosing and low dose daily dosing as part of chemoradiation therapy are allowed.
- **4.15** Patients receiving treatment with other antiepileptic medications will not be excluded. Vorinostat is not metabolized by cytochrome P450 3A4 (CYP 3A4). However, vorinostat may potentially suppress CYP 3A4 activity. Therefore, patients should preferably be treated with non-enzyme inducing anti-epileptic medications to avoid any potential interactions with vorinostat. However, the use of non-enzyme inducing anti-epileptic medications is not mandatory. If enzyme-inducing antiepileptic drugs are used, monitoring of drug levels should be considered, as considered clinically appropriate by the treating physician.
- **4.16** Patients with a known allergy to any component of vorinostat, or a known allergy to temozolomide and/or isotretinoin will be excluded.
- **4.17** Patients must be willing and able to comply with the FDA mandated iPLEDGE program for treatment with isotretinoin (cRA). Patients must sign specific informed consents for treatment with cRA, as mandated by iPLEDGE guidelines. Women of childbearing potential must not be pregnant, must not be breast-feeding and must practice adequate contraception (please refer to 6.4 and Appendix I for details and definitions woman of childbearing potential; adequate methods of contraception).
- **4.18** Male patients on treatment with vorinostat must agree to use an adequate method of contraception for the duration of the study, and for 30 days after the last dose of study medication (please refer to Appendix I for definition of adequate methods of contraception).
- **4.19** Patient must be able to tolerate the procedures required in this study including periodic blood sampling, study related assessments, and management at the

treating institution for the duration of the study. Inability to comply with protocol or study procedures (for example, an inability to swallow tablets) will be an exclusion criteria.

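### Criterion 4.18 asks only men on vorinostat for a contraception commitment, so it omits non-surgical Arm 2 men; secondarily, no pregnancy test is timed to the first pre-operative vorinostat dose

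*Combined protocol and SAP*

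**What the plan says.** **Men.** Section 4.18 reads: "Male patients on treatment with vorinostat must agree to use an adequate method of contraception for the duration of the study". It continues for 30 days after the last dose of study medication and refers to Appendix I for acceptable methods. Section 4.17 requires every patient to comply with the isotretinoin risk programme (iPLEDGE), but its explicit statement that patients "must practice adequate contraception" is addressed to women of childbearing potential.

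The drug sections go further than 4.18:

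- Section 3.2.7 (vorinostat side effects): "Both women and men of reproductive potential participating in vorinostat studies must be completely informed of the unknown risks of pregnancy". Women must undertake to avoid pregnancy, and men must undertake not to "father a child during the time they are participating in the study until at least 30 days after the final dose". It adds: "Further, appropriate contraception must be used".
- Section 3.3.9.6: "Temozolomide is potentially mutagenic and should be handled with appropriate precautions by both staff and patients".
- Section 3.3.11: "Treatment of a man with temozolomide may increase the risk of birth defects if he causes a woman to become pregnant" during his own treatment, and "Men receiving temozolomide should be directed to use effective contraception while they are being treated".

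Under 5.1.2, Arm 2 now combines temozolomide with isotretinoin. It contains no vorinostat.

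**Women in the surgical arm.** Section 5.2.2 gives ten patients vorinostat for three days, the last dose on the morning of surgery, and randomizes them about two weeks after surgery. Section 6.3 lists a pregnancy test in the pre-treatment panel, with a window counted from registration. Sections 6.3 and 7.5 both require a test 24 hours before isotretinoin. Section 7.9 schedules a blood sample before the first pre-operative vorinostat dose, for biomarkers only. Section 2.3.3 says pregnant women should not take vorinostat.

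**The concern.** Eligibility criteria are what a site checks before a patient enters. If the criterion is narrower than the safety text elsewhere in the protocol, a site that follows the checklist literally may not ask a man in Arm 2 for the commitment that the drug sections call for. The criterion also depends on a treatment that appears to be unknown when a non-surgical phase II man is screened, because 5.2.1 assigns the arm by randomization.

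For surgical-arm women, the test closest to a dose is attached to the second drug they receive rather than the first. In both cases the stake is fetal exposure to a drug that the protocol itself regards as hazardous in pregnancy. No endpoint, randomization rule or operating characteristic is involved.

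**Working it through.** The plan gives no figure on this point. The check compares the provisions group by group and then puts the pregnancy tests in time order.

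**Step 1. Which men does each provision reach?** Arm 1 phase I accrual is complete (5.1.1) and Arm 2 needs no phase I (5.1.2), so the remaining phase I patients are in Arm 3.

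| Men in | Vorinostat received? | 4.18 | 3.2.7 | 3.3.11 |
|---|---|---|---|---|
| Phase I, Arm 3 | yes | yes | yes | yes |
| Phase II, Arm 1 | yes | yes | yes | no temozolomide |
| Phase II, Arm 3 | yes | yes | yes | yes |
| Phase II, Arm 2, surgical | yes, pre-operatively | yes | yes | yes |
| Phase II, Arm 2, non-surgical | no | **no** | yes | yes |

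One group falls outside 4.18, and two other sections reach it.

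**Step 2. Do the provisions carry the same weight?**

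- 4.18 is a condition of entry, with a 30-day tail.
- 3.2.7 is mandatory and not limited by arm, with a tail of at least 30 days. It stands under the vorinostat heading.
- 3.3.11 is phrased as a recommendation, covers the treatment period only and gives no tail.

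For a non-surgical Arm 2 man, the 30-day tail therefore rests on 3.2.7 alone.

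**Step 3. How many men?** No sex split is given. The simulation tables give average patients per arm, but for both sexes and without separating surgical patients. The number cannot be computed.

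**Step 4. Order of events for a surgical-arm woman.** The sequence that 5.2.2, 6.3 and 7.5 imply is:

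1. panel test, in a window tied to registration;
2. registration;
3. pre-operative vorinostat;
4. surgery;
5. randomization, roughly two weeks later;
6. test 24 hours before isotretinoin;
7. isotretinoin.

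The test in item 6 follows the exposure in item 3, so it cannot guard against that exposure. Only the panel test can.

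**Step 5. How old can the panel test be?** The window is 14 days plus 3 working days. Three working days span 3 to 5 calendar days, depending on the weekday and ignoring public holidays. The limit at registration is therefore 14 + 3 = 17 to 14 + 5 = 19 calendar days. Age at the first vorinostat dose = age at registration + interval from registration to that dose. The plan does not state the second term, so the age at first dose cannot be determined.

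**The case against.** The strongest reply is that the protection already exists. Section 3.2.7 binds every man in the study and 3.3.11 directs contraception for men on temozolomide, so 4.18 merely fails to repeat an obligation found elsewhere. It names only vorinostat and may have been meant only to carry the vorinostat text in 2.3.3, which concerns partners of men taking that drug. Because the arm is unknown at screening, a site may in practice ask every man. All arms contain isotretinoin, so all men enter iPLEDGE and sign its consents. Appendix I and the consent pages, which are not in the supplied text, may contain further wording.

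On the secondary point, 4.17 bars pregnant women, 6.3 lists a pre-treatment test, and no section sets a 24-hour window for vorinostat.

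All of this stands as a limit on weight. It does not remove the mismatch in the criterion that sites apply, or the lack of a test timed to the first study-drug dose.

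Three stronger readings are tempting, and the documents do not support them:

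- A reader might infer that Arm 2 men are unprotected. Sections 3.2.7 and 3.3.11 say otherwise.
- A reader might infer that surgical-arm women need no pregnancy test before vorinostat. The 6.3 panel can be read as requiring one near registration.
- A reader might count the days from the first vorinostat dose to the isotretinoin test and call the result a minimum. Section 5.2.2 gives only an approximate interval, so it sets no floor, and that count is not the age of the panel test at first dose.

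**Conclusion.** The point holds as a minor misalignment. By its wording, 4.18 omits one group, non-surgical men in Arm 2, whom the protocol's own safety sections cover. Separately, no pregnancy test is timed to the first pre-operative vorinostat dose.

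The size is small. The number of men cannot be computed. The surgical part concerns at most 10 patients of both sexes, possibly with no women of childbearing potential.

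The conclusion assumes the plain reading of 3.2.7, under which a man in Arm 2 is taking part in a vorinostat study, and it assumes that non-surgical men are screened before randomization. It draws nothing from the absence of Appendix I or the consent pages, and nothing about what sites actually do. It also does not claim that 4.18 is left over from the replacement of carboplatin, because the superseded text is not shown.

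**What to change.** **Main change, 4.18.** Drop the condition on vorinostat. Every male patient should agree, at registration, to adequate contraception throughout the study and for at least 30 days after the last dose of any study drug. The 30-day period is already in 4.18 and 3.2.7, so no new duration is introduced, and the commitment no longer depends on the arm.

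**Secondary change, 5.2.2, 6.3 and 7.5.** Require a negative pregnancy test within a short stated window (24 hours would match the isotretinoin rule) before the first dose of any study drug, including pre-operative vorinostat. Keep the isotretinoin test. If the result can be ready before dosing, the sample can be taken with the pre-dose draw that 7.9 already schedules.

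**Cost.** Amendment and consent wording, plus one routine test for the few, possibly zero, women of childbearing potential among the 10 surgical patients. The statistical design is untouched.

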5.0 TREATMENT PLAN

5.1. Phase I Component

The Phase I component of the trial was designed with three treatment arms (see below). This component is a non randomized trial in which Arm 1 and Arm 2 were to be opened simultaneously with consecutive patients enrolled alternately to each arm, and sequentially to each dose level. If the MTD was reached earlier in one arm, all subsequent patients were to be enrolled to the other arm. Once the MTD for Arm 1 and Arm 2 was known, Arm 3 would begin accrual. A maximum of 54 patients were to be enrolled in this component of the trial. The MTDs obtained in the Phase I component were planned to be used as the Phase II dose in the next component of the trial.

5.1.1. Arm 1 – Vorinostat plus isotretinoin

This arm assessed the MTD of vorinostat in combination with a fixed dosage of isotretinoin (cRA) as shown in the table below. A cycle of treatment was 28 days (+ 3 days); the treatment schedule began with cRA on days 1-21. The total daily dose was to be given orally, divided BID (twice a day). Vorinostat was administered on days 1-14. The total daily dose was given once daily orally. Days 22-28 was considered as a no-treatment "rest" period.

A conventional phase I design was used with 3 patients enrolled into the first dose level and monitored for 3 weeks. If no DLT was seen, the next 3 patients were to be enrolled at the next dosage level. A maximum of three dosage levels will be utilized as shown in the table below. If no DLT was noted after dose escalation to Level III,

these doses were to be utilized for the phase II components of the study. If 1/3 patients shows \geq grade 3 toxicity, the cohort was to be expanded to 3 more patients, If 2/6 patients experience \geq grade 3 toxicity, the DLT was considered reached, and previous (lower) dosage level was to be declared as the MTD of vorinostat in combination with cRA.

Level	Arm 1		
	Vorinostat (mg/day x 14 days)	cRA (mg/m2/day x 21 days)	
0 (starting dose)	300 mg	100	
1	400 mg	100	
II	500 mg	100	

This arm of the trial completed accrual as planned and an MTD was established for the combination of vorinostat (400 mg/day on days 1-14) and isotretinoin (100 mg/m2/day on days 1-21) on a 28 day schedule. We propose to use this dose in the phase II trial.

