5.1.3. Arm 3 – Vorinostat plus isotretinoin plus temozolomide

This arm will assess the MTD of vorinostat and temozolomide in combination with fixed doses of cRA. The enrollment will proceed as outlined for Arm 1 and 2 (cohorts of 3 patients enrolled to each dose level), declaring MTD for vorinostat in combination with temozolomide and cRA once DLT is noted. In this arm, cRA will be given on days 1-21 and vorinostat on days 1-7 and 15-21. Temozolomide will be administered orally on days 1-7 and 15-21. Days 22-28 will be considered a notreatment "rest" period. A maximum of three dose levels of vorinostat will be used as shown in the table below.

Level	Arm 3		
	Vorinostat	cRA	Temozolomide
	(mg/day x days 1-7 &	(mg/m2/day x 21	(mg/m2/day on
	15-21)	days)	days 1-7 & 15-21

-111	300	100	100
-11	300	100	125
-1	400	100	125
0 (starting dose)	400	100	150
I	500	100	150

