5.3. Definition of dose limiting toxicities (DLT)

Toxicities will be graded according to the Common Terminology Criteria for Adverse events (CTCAE) Version 3.0. (see Appendix B). If multiple toxicities are seen, the presence of DLT should be based on the most severe toxicity experienced. DLT will be defined as any of the following events occurring during treatment and attributable to the study drugs:

5.3.1 Any grade 4 hematological toxicity excluding lymphopenia . (if the toxicity is Grade 4 neutropenia without fever, it must NOT resolve/regress to \leq Grade 1 within 7 days of onset to be considered a DLT).

5.3.2 Any non-hematologic grade 3 toxicity, weight gain (in patients on steroids), alopecia, and venous thromboembolic disease *. Grade 3 nausea, vomiting, or diarrhea that cannot be controlled by medical therapy will be considered dose-limiting. Isolated laboratory abnormalities not of clinical significance will be discussed with the IRB and the decision to declare these DLTs will be based on the IRB recommendations.

5.3.3 Failure to recover from toxicities to be eligible for re-treatment within 4 weeks of the last dose of the drugs.

*Non-Relevant Toxicities for Brain Tumor Protocols

Lymphopenia is a common finding among patients with primary brain tumors and is directly attributable to concurrent use of corticosteroids. To date, even Grade III lymphopenia has not been associated with a worsening of clinical outcome. Therefore, we will not consider this parameter in the determination of optimal dosing of drugs.

Weight gain is a common finding among patients with primary brain tumors. This too is directly attributed to the concurrent use of corticosteroids. Doses of steroids or study agents will not be modified as a consequence of weight gain. Corticosteroid dosage will be based on maintenance of control of edema in the brain and the standard clinical practice to use the minimal effective dose of corticosteroids will be employed.

Alopecia is a common occurrence in patients with brain tumors as a consequence of cranial radiotherapy. Alopecia will not be recorded or graded as toxicity.

Venous thromboembolic disease is a common complication occurring in up to 30% of patients with malignant gliomas [32, 33]. In this study, patients who develop deep vein thrombosis may receive anticoagulation and resume therapy once they are stable on anticoagulation. Grade III deep vein thrombosis will not be considered a DLT.

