Dose reductions: If any treatment related non-hematologic AE observed was grade > 2 (except alopecia, lymphopenia, nausea, vomiting, weight gain and DVT/PE) and/or if platelets < 50×10^{9} /L and/or ANC < 1×10^{9} /L, then the dose should be reduced by one dose level. Patients who require more than three dose reductions will have treatment stopped.

If any treatment-related non-hematologic AE observed was grade 4 (except alopecia, lymphopenia, nausea, vomiting, weight gain and DVT/PE) then temozolomide treatment should be stopped.

Subsequent cycles: Any dose reductions of temozolomide will be determined according to: (1) non-hematologic AE during the preceding

treatment cycle, as well as (2) the lowest ANC and platelets observed. No dose escalation should be attempted. The same dose reductions as for the second cycle should be applied. Important: If the dose was reduced or delayed for AEs, there will be no dose re-escalation in subsequent treatment cycles.

Summary of Dose Modifications or Discontinuation for Temozolomide-Related Adverse Events

Worst Treatment-Related Non-Hematologic AE (except for alopecia, nausea, and vomiting) During the Previous Cycles			
Grade	Dose Modification		
0-2	No dose modifications for non-hematologic AEs. Dose reductions based on ANC and platelet counts are applicable.		
3	Reduce by one dose level (except alopecia, lymphopenia, nausea, vomiting, weight gain and DVT/PE).		
4	Stop (except alopecia, lymphopenia, nausea, vomiting, weight gain and DVT/PE). Dose modifications based on ANC and platelet counts are not applicable.		

Worst Treatment-Related Hematologic AE During the Previous Cycle

Worst A	ΑE	Platelets		
		≥100 x 10 ⁹ /L	50 – 99 x 10 ⁹ /L	< 50 x 10 ⁹ /L
	≥ 1.5 x 10 ⁹ /L	Dose unchanged	Dose unchanged	Reduce by 1 dose level
ANC	≥1 & <1.5 x 10 ⁹ /L	Dose unchanged	Dose unchanged	Reduce by 1 dose level
	< 1 x 10 ⁹ /L	Reduce by 1 dose level	Reduce by 1 dose level	Reduce by 1 dose level

Note: A complete blood count must be performed on days 14 and 28 (\pm 72 hours) after the first daily dose of each treatment cycle.

Hematologic AE on Day 1 of Each Cycle (within the prior 72 hours before Day 1)			
AE	Delay		
ANC< 1.5 x 10 ⁹ /L and/or Platelet count < 100 x 10 ⁹ /L	Delay up to 4 weeks until all resolved. If unresolved after 4 weeks then stop. If resolved, dose delay/reductions based on non-hematologic AEs are applicable. If treatment has to be delayed for AEs, then no escalation is possible.		

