11.0 STATISTICAL CONSIDERATIONS

11.1 Phase I component

The phase I component will be a non randomized trial in which Arm 1 and Arm 2 will be opened simultaneously with consecutive patients enrolled alternately to each arm, and sequentially to each dose level. If the MTD is reached earlier in one arm, all subsequent patients will be enrolled to the other arm. Once the MTD for Arm 1 and Arm 2 is known, Arm 3 will begin accrual. A maximum of 54 patients will be enrolled in this component of the trial. The MTDs obtained in the Phase I component will be used as the Phase II dose in the next component of the trial.

11.1.1. Arm 1 of the phase I component was to assess the MTD of vorinostat in combination with a fixed dosage of cRA as shown in the table below. As noted above in section 5.1.1, the MTD of vorinostat in combination with cRA has been established in the current trial.

Level	Arm 1				
	Vorinostat cRA				
	(mg/day x 14 days) ((mg/m2/day x 21 days)				
0 (starting dose)	300	100			
1	400	100			
II	500	100			

11.1.2. Arm 2 of the phase I component was aimed at assessing the MTD of Carboplatin (CBT) in combination with a fixed dosage of cRA. With the change in the combination to temozolomide with isotretinoin, the MTD is already known; hence, a phase I trial of this arm will not be needed.

11.1.3. Arm 3 of the phase I component will assess the MTD vorinostat in combination with fixed doses of temozolomide + cRA. For temozolomide, the Phase II dose determined in Arm 2 will be used. The enrollment will proceed as outlined for Arm 1 (cohorts of 3 patients enrolled to each dose level), declaring MTD for Temozolomide in combination with vorinostat and cRA once DLT is noted.

Level	Arm 3		
	Vorinostat (mg/day x days 1-7 and 15-21)	cRA (mg/m2/day x 21 days)	Temozolomide (mg/m2/day on days 1-7 &15-21
-111	300	100	100
-11	300	100	125
-I	400	100	125
0 (starting dose)	400	100	150
I	500	100	150

- If the initial cohort of patients at starting dose level 0 do not experience DLT, the next cohort of patients will be treated by dose escalation to level I (with increase in the dose of vorinostat). If no patients experience DLT in this cohort, 3 more patients will be enrolled to expand this cohort to a total of 6 patient to confirm that MTD has been achieved. If no DLT is noted or if only 1/6 patients experience DLT after this expansion of level I, this dose level will be declared the MTD and hence the phase II dose.

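### The only stated phase I observation period is 3 weeks, too short to declare some of the protocol's own DLTs; Arm 3 either inherits it or has no stated period

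*Combined protocol and SAP*

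**What the plan says.** Section 5.1.1 (Arm 1, now complete) sets the cohort procedure: "3 patients enrolled into the first dose level and monitored for 3 weeks", followed by "If no DLT was seen, the next 3 patients were to be enrolled at the next dosage level". The same section gives the cycle length: "A cycle of treatment was 28 days (+ 3 days").

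Arm 3 takes its procedure by cross-reference. Section 5.1.3 has "The enrollment will proceed as outlined for Arm 1 and 2 (cohorts of 3 patients enrolled to each dose level"), and section 11.1.3 has "The enrollment will proceed as outlined for Arm 1 (cohorts of 3 patients enrolled to each dose level"). In Arm 3 isotretinoin is given on days 1 to 21 and vorinostat on days 1 to 7 and 15 to 21; for the third drug, "Temozolomide will be administered orally on days 1-7 and 15-21". Days 22 to 28 are a rest period. The Arm 3 escalation and de-escalation rules (5.1.3.1, 5.1.3.2, repeated in 11.1.3) give patient counts but no observation time.

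Section 5.3 counts attributable events during treatment, without naming a cycle or a number of days. Two of its items need time to pass. Under 5.3.1, grade 4 neutropenia without fever is a DLT only if it has not come down to grade 1 or less within 7 days of onset. Under 5.3.3, the criterion is "Failure to recover from toxicities to be eligible for re-treatment within 4 weeks of the last dose of the drugs". Section 5.4.2.3 adds "A complete blood count must be performed on days 14 and 28", with a tolerance of 72 hours.

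**The concern.** An escalation rule and a DLT definition have to work on the same clock. If a cohort is cleared before an event can be classified, a patient with an emerging DLT is counted as free of DLT when the decision is made. The next cohort may then be treated at a higher dose too early. The declared MTD becomes the phase II dose, so timing at expansion and at MTD declaration matters as well.

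The protocol's own background gives this some weight. Section 2.11 reports that the earlier three-drug combination, with carboplatin, was not tolerated at its starting level or at two lower levels. Section 2.6 says that dose-dense temozolomide with vorinostat had not yet been explored. Section 2.3.4.1 says that most vorinostat DLTs came within the first month, and gives no split at 3 weeks.

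**Working it through.** The 3 weeks is a design choice, so there is no derived figure to reproduce. The check is day arithmetic, followed by one illustration.

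**Inputs**
- Observation period: 3 × 7 = 21 days (5.1.1).
- Cycle length: 28 days (5.1.1).
- Last Arm 3 dosing day for all three drugs: day 21 (5.1.3).
- Afebrile grade 4 neutropenia: 7 days from onset (5.3.1).
- Failure to recover: 4 × 7 = 28 days from last dose (5.3.3).
- Late blood count: day 28 ± 3 days (5.4.2.3).

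**If Arm 3 inherits the 3 weeks**
- Days between the last dose and the end of the period: 21 − 21 = 0.
- Part of the cycle left outside: 28 − 21 = 7 days, or 7/28 = 25%. This is the whole rest week.
- Earliest date of the day-28 count: 28 − 3 = day 25, after the period has closed.
- Latest onset of afebrile grade 4 neutropenia that can be classified by day 21: 21 − 7 = day 14. Onsets on days 15 to 21, during the second vorinostat and temozolomide block, become classifiable only on days 22 to 28.
- First day on which 5.3.3 can be met: last dose day + 28. That is day 49 after full dosing (21 + 28), day 35 if dosing stopped on day 7 (7 + 28), and day 29 if only day 1 was given (1 + 28). None falls within 21 days.

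**If Arm 3 does not inherit the 3 weeks**

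Neither 5.1.3 and its subsections nor 11.1.3 states a period. The phrase about treatment in 5.3 sets no length and does not hold back the next cohort.

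**Illustration, one escalation step only**

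Let p be the true DLT risk per patient and s the share of DLTs that cannot be declared by day 21. Then P(0 of 3 seen) = (1 − p(1 − s))³. The documents give neither p nor s, so both are assumptions. With p = 0.33:

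| Late share s | Visible risk p(1 − s) | P(0 of 3 seen) |
|---|---|---|
| 0 | 0.330 | 0.670³ = 0.30 |
| 0.10 | 0.297 | 0.703³ = 0.35 |
| 0.25 | 0.2475 | 0.7525³ = 0.43 |
| 0.50 | 0.165 | 0.835³ = 0.58 |

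**The case against.** The other side has several good points.

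- The 3-week sentence is in the past tense and belongs to a finished arm. The parenthesis in 5.1.3 and 11.1.3 names only cohorts of 3, so the cross-reference may carry cohort size and nothing else. This stands: inheritance is an inference. It changes the defect from a conflicting period to a missing one.
- Section 7.1 requires weekly blood counts (± 3 days) in cycle 1. Neutropenia starting in days 15 to 21 could therefore be visible at the decision even though it is not yet classifiable. This stands, but nothing tells the investigator to wait for it.
- Most DLTs need no waiting. Other grade 4 haematological events and qualifying grade 3 non-haematological events can be declared at onset. Section 5.3.3 acts alone mainly for persistent lower-grade toxicity. This stands and narrows the problem.
- A full 28-day period would not reach 5.3.3 either. This is true, and it shows that the definition and the period need to be settled together.
- Phase II reviews DLTs after every 10 patients per arm (9.1, 11.2). This limits the consequences of a dose set too high, but only after patients have been treated at it.

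A reader might go further and infer that Arm 3 will escalate blind, or that the declared MTD will be too high. The documents do not support that. There is one upward step, from level 0 to level I. Level I cannot be declared the MTD on 3 patients: with no DLT in the first 3 it is expanded to 6, and at most 1 of 6 may have a DLT (5.1.3.1). The first three would be followed past day 21 while the second three are observed, and 5.3 does not bar their later events from the tally. The 30% to 58% range therefore must not be read as a probability of a wrong MTD.

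**Conclusion.** The point holds in a limited form. On one reading, the stated 3-week period conflicts with parts of the stated DLT definition. On the other, Arm 3 has no stated period. On either reading, no rule makes a cohort wait for a pending event, and none says how a DLT declared after escalation counts toward the level already cleared.

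The affected events are afebrile grade 4 neutropenia with onset after day 14, anything first appearing in the rest week, and all failures to recover under 5.3.3. The day arithmetic rests only on protocol figures. The change from 30% to as much as 58% at the single escalation step rests on an assumed 33% DLT rate and an assumed late share of up to one half. It also treats late events as unseen at that decision; it does not describe the final 6-patient tally. The matter should be settled before Arm 3 cohorts are judged, because it bears on patient safety and on the choice of phase II dose.

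**What to change.** Reconcile 5.1.1, 5.1.3, 5.1.3.1, 5.1.3.2 and 11.1.3 with 5.3, and do two things:

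1. State for Arm 3 the period that must finish before each escalation, de-escalation or MTD decision, so that it agrees with the events counted as DLTs. The clinical team chooses the period and the definition; no period is proposed here.
2. State how a pending event is handled at a decision, and how a DLT declared after the next cohort has opened enters the tally of the earlier cohort.

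The cost is protocol wording. If the chosen period is longer than 3 weeks, each cohort decision comes somewhat later. No change to cohort sizes is required.
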